Provide a brief description of the study design or data collection methodologies. Details regarding protocol specific research procedures will be discussed in a later section.

Design: A two-arm randomized trial.

Randomization:

- Eligible households with at least one child (reference child) in the BGCAA after-school program whose caregiver/parent (guardian) (reference caregiver) consents to participate in the study will be randomized to either the active intervention or the control (1:1 ratio). Randomization will be stratified by the family's SNAP beneficiary status as SNAP could affect uptake of treatment elements offered in the family support arm.

Blinding: Outcome assessors, principal investigator, and biostatistician are blinded to participant allocation. Participant and other staff are unblinded.

Study arms (19 weeks) (Figure 1):

Randomized arms

Children in both intervention and control arms participate in the BGCAA's after-school program with CATCH curriculum.

1. Across participating school sites, the whole BGCAA's after-school program runs for 3h, Mon-Fri for the school year. Children enrolled are expected to attend a minimum of 2x/week.
2. CATCH curriculum will be delivered as a component of the after-school program in blocks of 45-60 min, twice a week.
3. Children also participate in active recreational time (approx. 60 min, offered 1x/week at a minimum) which consists of a mixture of free play, structured physical activity games, and/or sports activities (including soccer, football, and basketball).

Intervention arm: BGCAA after-school program + Family support

1. Children participate in the BGCAA's after-school program with CATCH curriculum as described above.
2. The child's caregiver will receive the following:
 - Family tip sheets sent via mobile text at the start of the program and then every 3 weeks, to a total of 6 txt messages.
 - Weeks 1-4 (4 weeks):
 - i. Welcome package mailed to the family's residence approximately in the first week of the program.

- ii. Weekly: 1 box of produce
- iii. Recipes accompanying each box (sample recipe card attached to submission)
- iv. Bi-Weekly: Grocery store gift cards (2x \$20, to a total of \$40)
- Weeks 5-19 (total of 10 weeks over the 19-week study timeline):

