 - i. For five weeks, an optional online form (or “*goal sheet*”) will be sent to the parent/caregiver (5 sheets in total) with questions about trying new FV items to be completed within the next 7 days. As an incentive, a \$10 gift card will be sent the following week to those who complete it (a potential total of \$50).
 - ii. Week 11: \$20 Grocery store gift card. Based on disruptions due to the school year breaks, we will provide an extra \$20 gift card to re-engage the week after a school holiday.

Control arm: BGC after-school program only

1. Children participate in the BGCAs after-school program with CATCH curriculum as described above.
2. At the end of the study, they will receive \$120 as grocery store gift cards.

[figure not shown]

Figure 1. Study design: 2 randomized arms

Outcomes:

- Primary:
 - Child's diet quality: measured by Healthy Eating Index, HEI, scores calculated from the Texas School Physical Activity and Nutrition (SPAN), 2nd Grade.
 - Child's fruits and vegetable consumption, measured by SPAN, 2nd Grade.
- Secondary outcomes:
 - Caregiver/parent diet quality, measured by HEI scores calculated from the SPAN, 8th Grade.
 - Child's physical activity levels
 - Child's body mass index, as percentile of BMI-for-age

Study measurements:

Timepoint measurements for all study participants (child-parent dyads) include:

- baseline (approximately up to 4 weeks prior to the first produce bag and grocery store gift card being distributed). Height and weight will be taken during the first 1-2 weeks of the research program start date during a BGCAA field day.
- mid-point (planned for approximately weeks 5-8)
- end-point (approximately between weeks 16 and 21). Height and weight will be taken during the 19th week of the program at the BGCAA's field day.

Outcomes	Tool	Time points	Administration
Child's Diet (primary)	TX SPAN 2 nd grade 2019-2020 – Dietary questions	Baseline, Mid-point, End point	Child, Guardian-reported Structured interview over the phone by RA
	SPAN Healthy Eating Index scores (includes total, healthy, and unhealthy scores)	Baseline, Mid-point, End point	Child, calculated from SPAN
Physical Activity	TX SPAN 2 nd grade 2019-2020 – Physical activity questions	Baseline, End point	Child, guardian-reported Structured interview over the phone by RA
	Physical Activity Questionnaire – Children		

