Sedentary Behavior	TX SPAN 2 nd grade 2019-2020 – Sedentary behavior questions	Baseline, Mid-point, End point	Child, guardian-reported Structured interview over the phone by RA
Child's mental health	Strengths and Difficulties Questionnaire (SDQ)	Baseline, Mid-point, End point	Child, guardian-reported Structured interview over the phone by RA
BMI-to-age			
Weight	Weight scale	Baseline, End point	Intervention and control arms only: Measured by study staff
Height	Stadiometer	Baseline, End point	Intervention and control arms only: Measured, by study staff
Parent/Guardian's diet	NHANES 2009-2010 Dietary Screening Questionnaire	Baseline, Mid-point, End point	Parent, self-report Structured interview over the phone by RA
Parent/guardian's quality of life (physical/mental)	Short Form 12 (SF-12)	Baseline, End point	Parent, self-report Structured interview over the phone by RA

Pop descriptors (Baseline only)	Tool	Administration
Demographics & social needs (PRAPARE)	Customized. Related to: 1. parent/caregiver (age, gender, ethnicity, health insurance, work status, transportation and housing)	Parent, Self-report Structured interview over the phone by RA

	
 2. household (income, housing, program participation like SNAP, shopping and food prep) 3. child (sex, DOB, health insurance, program participation like SLP or SBP, previous BGCAA programs) 	
Food security	USDA 6-items	Parent, Self-report Structured interview over the phone by RA

5 Data Analysis

Describe the data analysis plan, including any statistical procedures or power analysis.

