Because both the primary and secondary outcome measures are continuous, normally distributed measures, we anticipate having to rely on normal theory analytic methods. Specifically, mixed linear regressions on the primary (HEI) and secondary outcome measures (such as Fruits & Vegetable subscores, BMI and parent HEI) will be fitted to test differential trajectories for two groups from baseline to midpoint and end point assessment of the program, time expressed as days elapsed from baseline. These models readily accommodate differential dropout in the arms with maximum likelihood estimation, random intercepts, and also adjust for any clustering effect of the BGCAA sites. Because randomization will be stratified by whether the family are SNAP recipients or not, the main effect of family's SNAP beneficiary status will be included in all models in addition to the main target terms of interest: two-way interactions of time X treatment, time X SNAP, and their three-way interaction. Overall alpha will be set at 0.05 for each child outcome on these target terms.

In addition to these intention-to-treat (ITT) analyses we will also conduct as-treated (AT) analyses incorporating the 'dose' variable that will be formed based on implementation database elements that permits the tracking of program elements consumed/ picked up/ attended by the target child and his/her parent/guardian in the two active arms. In AT models, total dose taken-up by the end of the program will enter into product terms with time. As is typical, we expect the AT models to have greater sensitivity/ precision in estimating the added value of the family support beyond the elements of the after-school program with CATCH for change in HEI and secondary outcomes. In addition the dose variable sheds light on the effects of Boys and Girls Club programming, including CATCH, regardless of other incentives. Statistical controls for family demographic characteristics, food insecurity, child age, sex, and SNAP beneficiary status will be included in the AT framework as 'dose' is not completely controlled by the randomization and hence would be expected to be correlated with these characteristics (e.g. economically disadvantaged families may be more likely to uptake more of the program elements).

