 - With n=113 households in each active arm, we can detect a moderate effect size $d = .45$.
 - Considering 15% attrition in each arm, we would end the study with n=96 in each active arm and able to detect an effect size of $d = .49$.
- If we successfully enroll 50%, N=150
 - With n=75 in each active arm, we can detect a difference of moderate effect size $d = .55$.
 - Considering 15% attrition, n=64 in each arm enable us to detect an effect size of $d = .60$.

Therefore, we will invite to participate in the study all households with at least one eligible child to maximize our ability to detect meaningful mean differences in children's HEI between the two active arms.

SCREENING AND RECRUITMENT

16

Identification and Screening

*Check the box below if this study involves a screening process **prior** to the informed consent process.*

This study involves obtaining information or biospecimens for the purpose of screening, recruiting or determining eligibility of prospective subjects prior to informed consent by either:

- 1. Oral or written communication with the prospective subject or LAR**
- 2. By accessing records containing identifiable private information or stored identifiable biospecimens.**

17

Identification and/or Screening Procedures

Describe the identification and/or screening procedures below.

The Identification of interested families will be done both by the BGCAA staff and our study staff through the various places where BGCAA can be reached, as follows:

- Distribution of flyers containing a QR code that links to an interest form to request more information later – at BGCAA sites & digitally via Class Dojo app that BGCAA staff use to communicate with families. In this form, if collecting interest information, we will collect the parent/guardian name, child name, school and/or afterschool site they attend, contact phone number, grade child will be in the fall, and preferred language. The path the QR code takes

them will be to a secure and HIPAA-compliant database (UT Box, REDCap, and/or UT Qualtrics) that will securely house the information to be filled out by the parent/guardian.

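### The BMI outcome is defined as a percentile, which does not fit the planned normal-theory model and down-weights heavier children; a BMI-for-age z-score from the same data would serve better.

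*Combined protocol and SAP*

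**What the plan says.** Section 4 (Design and Methodology, secondary outcomes) gives the BMI outcome as "body mass index, as percentile of BMI-for-age". The outcomes table in the same section labels it BMI-to-age, with weight and height measured at baseline and end point only.

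Section 5 (Data Analysis) opens with "Because both the primary and secondary outcome measures are continuous, normally distributed measures" and rests its choice of normal-theory methods on that statement. It then says that mixed linear regressions on the primary and "secondary outcome measures (such as Fruits & Vegetable subscores, BMI and parent HEI) will be fitted", with time by treatment among the target terms. The word used there is BMI, without a scale. No z-score, transformation, residual check or alternative model for BMI appears anywhere.

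The inputs for a z-score are already collected. For the end point, "Height and weight will be taken during the 19th week of the program", and there is a matching baseline measurement at the start of the programme. The baseline descriptors include "child (sex, DOB, health insurance" and other items, so sex and date of birth are on file.

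**The concern.** A percentile is a rank against a reference population. In a sample that matches the reference it is uniform on 0 to 100. In a heavier sample it is left-skewed against the ceiling. Section 5's distributional statement is therefore untrue for this outcome on the only scale the plan defines.

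The practical issue is less the shape than the unequal spacing. The same shift in BMI status is a large percentile change in the middle of the range and a small one near the top. A mean percentile change therefore gives progressively less weight to heavier children. A null BMI result could partly reflect the scale, and a non-null one would mainly describe mid-range children. Section 15 says recruitment is limited by the partner's capacity, so lost efficiency could not easily be made up by enrolling more children.

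**Working it through.** The documents give no effect size, SD, baseline distribution or power for BMI, so there is no BMI figure of the plan's own to reproduce. Inputs below marked *assumed* are not in the documents.

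**1. Shape.** With percentile = 100·Φ(z) and z standard normal, the percentile is uniform: mean 50, SD 100/√12 ≈ 28.9, excess kurtosis −1.2. For *assumed* baseline z means of 0.5, 0.8 and 1.2 with SD 1.1, simulated skewness is −0.51, −0.83 and −1.31. None of these is normal.

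**2. Compression.** Percentile change for a fall of 0.1 z = 100·[Φ(z) − Φ(z − 0.1)].

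| Starting percentile | z | Change in points | Relative to the median |
|---|---|---|---|
| 50th | 0 | 4.0 | 100% |
| 85th | 1.036 | 2.5 | about 62% |
| 95th | 1.645 | 1.1 | about 28% |
| 99th | 2.326 | 0.3 | about 8% |

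**3. Efficiency.** Relative efficiency is the squared ratio of the standardised treatment effects on the two scales, found by simulation. *Assumed*: baseline z mean 0 to 1.0, SD 1.0 to 1.2, baseline-to-end correlation .95.

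- Uniform effect of 0.1 z: the percentile has about 73 to 87% of the z-score's efficiency. At the retained size in one of section 15's scenarios ("we would end the study with n=96 in each active arm"), that is like analysing 0.73 × 96 ≈ 70 to 0.87 × 96 ≈ 84 children per arm on the z scale.
- Hypothetical effect only in children above the 85th percentile: about 18 to 29% for a 0.1 z effect, and 22 to 34% for 0.25 z.

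Baseline-adjusted and change-score analyses give nearly the same values. The loss is larger when the sample is heavier at baseline. The ends of the ranges move slightly with simulation details, so read them as approximate.

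**4. Power, as an illustration.** Two-arm comparison of baseline-to-end change, which is what a time by treatment contrast reduces to with two time points. n = 96 per arm, two-sided 0.05 (section 5 sets 0.05 per child outcome; two-sided is *assumed*). Also *assumed*: baseline SD 1.1, within-child change SD 0.3 z, uniform effect −0.12 z. Site clustering is ignored.

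- z scale, by formula: 0.12 / (0.3 × √(2/96)) = 0.12/0.0433 = 2.77, and Φ(2.77 − 1.96) = Φ(0.81) ≈ 79%. Simulation with 20,000 replicates gives 78 to 79%.
- Percentile scale, same simulated children: 71%, 67% and 62% for baseline mean z of 0, 0.8 and 1.2.
- No effect: rejection rate about 5% on both scales.

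**The case against.** Several points on the other side are sound.

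- **The modelled scale is partly inferred.** Section 5 says only BMI. Reading section 4's percentile into it is reasonable, because no other scale is defined. Even so, part of the defect is that the two sections do not name the same scale.
- **The mixed model does not need a normal raw outcome.** Its assumptions concern residuals and random effects. A reader might infer that a bounded outcome makes the test invalid. The simulation does not support that, since type I error stays near 5%. The case rests on weighting and sensitivity.
- **Heavier children are not ignored.** A reader might infer that children with high BMI contribute almost nothing. That is fair only from about the 99th percentile up. At the 85th the contribution is still about 62% of that at the median, and at the 95th about 28%. The documents do not say how many children lie that high.
- **The largest losses are hypothetical.** Efficiency of 18 to 34% requires an effect confined to children above the 85th percentile, and it varies with the size of that effect. The plan posits no such pattern and names no such subgroup.
- **It is one secondary outcome.** The hypothesis concerns child diet, and section 15 sizes the study on HEI and a dose-response correlation, never on BMI.

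These limit the size of the point but do not remove it. None of them gives a reason to prefer the percentile for modelling.

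**Conclusion.** The point holds in a limited form. The percentile is the only BMI scale the plan defines, it contradicts the stated normality premise, and it weights children unequally. The compression figures follow directly from the definition of a percentile, given normal z. The efficiency figures depend on the assumed baseline z mean, SD and correlation, none of which the documents supply. The uniform-effect result of about 73 to 87% is the one to carry forward, because it needs no assumption about who responds. In every case examined the z-score was the more sensitive scale.

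No primary conclusion and no error rate is at risk. This is a free improvement, not a flaw that threatens the trial.

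**What to change.** In section 4 (secondary outcomes and outcomes table) and in section 5, name the BMI-for-age z-score as the analysed outcome. Keep the planned mixed model with its time by treatment term: a scale problem does not call for a change to a baseline-adjusted model. State which growth reference is used, and that age is computed from date of birth at the date of each height and weight measurement. Report percentiles descriptively. In section 5, drop or qualify the blanket normality statement.

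The cost is wording only, since height, weight, sex and date of birth are already collected. There are two small downsides. Z-scores are less familiar to lay readers, which the descriptive percentiles address. Depending on the growth reference, z-scores may also still compress at extreme BMI, so a sensitivity analysis on a scale suited to very high values would be prudent.

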The greatest opportunity lies in exploratory analyses of the two randomized arm participants that permit the estimation of dose-response based on family characteristics. Both the "after-school program with CATCH" and the "after-school program with CATCH + family support" intervention arms are expected to show variation in dose. In the case of dose for "after-school program only"

participants, we expect dose variation to be predicted by structural characteristics of family routines (e.g. number of days the target child attends BCG after-school program is predicted by whether both parents are employed, family income, number of siblings and caretakers in the family as alternatives to BCG attendance). In contrast, dose for “after-school program with CATCH + family support” participants is more complex and includes distinct elements that require greater motivation on the part of the parent/ guardian to engage with (e.g. completing goal sheets and receiving incentives versus not completing incentivized elements of the program). We will model the associations of separate aspects of ‘dose’ with response (HEI, physical activity) and predict separate aspects of ‘dose’ from family characteristics at baseline. These exploratory analyses will provide clues on how to structure future programs, incentivize participation, as well as inform who is likely to benefit the most. In the exploratory analytic framework, we will engage in omnibus correction for inflations in type-I error rate and will not interpret any significant single result unless at least 10% of all examined associations are significant.

STUDY ELEMENT IDENTIFICATION

6 Study Elements

Check each research procedure included in your study.

A full description of all study procedures should be provided in the Procedures (Details) section below.

Procedures denoted with “” below have supplemental forms. Navigate to the [UTRMS-IRB Library, Templates](#) tab to download the applicable supplemental form.*

 Bio-specimens*	 Biometrics	 Registry or Repository*
 Focus Group	 Genetic Analysis	 Genomic Data Sharing
 International Research*	 Interview/Survey	 MRI

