We will invite all families across all 11 participating sites. Given numbers from the current year, we expect total number that could be invited (meeting inclusion/ exclusion criteria) to be 350 total index parent and child pairings. Below we discuss various realistic recruitment and retention scenarios given the capacity of our partner, BGCAA. Our aim will be to maximize recruitment but are prepared for various recruitment scenarios.

15 Sample size rationale

Describe your sample size rational below.

We are conducting both as-treated (AT) and intention-to-treat (ITT) analyses.

To inform our sample size calculations and power for the ITT and AT analyses, we relied on information from the pilot trial conducted at BGCAA sites in the spring of 2021. The pilot also used the SPAN tool to measure diet for child and caregiver (Kahlon et al., 2022).

For the AT analysis, we use the results of the pilot from Spring of 2021 showing a dose response correlation, which was $r = 0.31$. We have 80% power to detect this association with total $N = 79$. Even if the enrollment and retention is as low as $n = 64$ for each active arm, we would be able to detect a dose-response correlation as low as 0.24 in the AT framework.

From the 2021 study, the effect size for the overall child's HEI (Healthy Eating Index) at the end of the study was .47 with an ICC of .20 for person x site clusters. For the present study, to be able to detect an identical difference between the two randomized arms (Program+Family Support and After-school program only) with 80% power at $\alpha = .05$, we would need to retain 120 children in each arm. Considering a 15% attrition rate, a target recruitment of approx. 140 children into each active arm would permit sufficient power to observe the targeted moderate group difference.

Given the recruitment pool for our sample is limited by the BGCAA program capacity, we estimated the changes in effect sizes (i.e., our ability to detect differences) in two scenarios, maintaining 80% power at $\alpha = .05$.

Assuming that all eligible households will be invited to participate and that a conservative potential pool of approx. **300 households** will be maintained in the fall (in the current school semester, Boys and Girls Club has approximately 313 households attending their after-school program with at least one child), we can expect the following:

- If we successfully enroll 75% in the study, N=226

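### Section 5 sets an overall alpha of 0.05 on three target terms without reserving it for the single arm difference that the trial is powered to test

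*Combined protocol and SAP*

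**What the plan says.** Section 5 plans mixed linear regressions that compare how the two arms change from baseline through the mid-point to the end point, with "time expressed as days elapsed from baseline". Besides a main effect of SNAP status, the models carry the "main target terms of interest: two-way interactions of time X treatment, time X SNAP, and their three-way interaction". The alpha rule follows at once: "Overall alpha will be set at 0.05 for each child outcome on these target terms". The section does not say how that alpha is allocated, in what order the terms are tested, whether the test is joint, or how SNAP is coded. The only multiplicity rule is confined to other analyses: "In the exploratory analytic framework, we will engage in omnibus correction for inflations in type-I error rate".

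The rest of the protocol is simpler. Section 2 states one hypothesis: adding caregiver resources to the after-school curriculum improves child diet more than the curriculum alone. Section 15 sizes the intention-to-treat comparison "to be able to detect an identical difference between the two randomized arms" with 80% power at alpha .05, from a pilot effect on child HEI that "at the end of the study was .47 with an ICC of .20". SNAP status enters the design in section 4 as the stratification factor, because it could affect uptake of the family support.

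**The concern.** An overall error rate attached to several terms is naturally read as shared among them. The sample size, however, gives all of .05 to one comparison. Both statements can be true only under a testing order that the plan does not give.

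Time x SNAP compares trajectories of SNAP and non-SNAP families. It belongs in the model as a lower-order term, but no result on it could support or refute the hypothesis, so it has no claim on confirmatory alpha.

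Naming time x treatment would not by itself settle the test. With the three-way term in the model, the meaning of that coefficient changes with the SNAP coding. Time is modelled in days over three visits, whereas the powered effect is an end-of-study difference and section 4 lets the end-point visit fall between about weeks 16 and 21. Analysts who all follow section 5 could therefore report different p-values for the trial's main question, and the choice could be made after the data are seen.

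**Working it through.** **Inputs.** From section 15: d = .47, ICC = .20, 80% power, alpha .05, 120 retained per arm. From section 5: three target terms, overall alpha .05. Two-sided testing is assumed, as sidedness is not stated. The SNAP share is not in the documents; 30% to 70% is assumed where needed.

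**The plan's own figure.** Without clustering, n per arm = 2 x (1.960 + 0.842)^2 / .47^2 = 71.1, so 72. Reaching 120 needs a variance inflation of 120/71.1 = 1.69. The protocol gives no cluster size, and the usual ICC factors do not give 120: 1 + ICC gives 86, 1/(1 - ICC) gives 90, and clusters of 4 or 5 give 115 or 130. The four enrolment scenarios in section 15 imply 1.45 to 1.47. The figure of 120 is therefore not reproduced. The main calibration takes the plan at its word: 120 per arm gives 80% at two-sided .05, so the noncentrality is 1.960 + 0.842 = 2.802.

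**Power for the arm difference under each reading.** For a single test at level a, power = Phi(2.802 - z(1 - a/2)). Joint tests use a noncentral chi-square with noncentrality 2.802^2, assuming that only the arm difference exists.

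| Reading of the overall 0.05 | Calculation | Power |
|---|---|---|
| Time x treatment first, full .05 | Phi(2.802 - 1.960) | 80% |
| Split over the two treatment terms (.025 each) | Phi(2.802 - 2.241) | 71% |
| Split over three terms (.0167 each) | Phi(2.802 - 2.394) | 66% |
| Joint test, 2 df | noncentral chi-square | 71% |
| Joint test, 3 df | noncentral chi-square | 64% |

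**Second calibration.** With the design effect of about 1.46 implied by the section 15 scenarios, the noncentrality at 120 per arm is .47 x sqrt(120 / (2 x 1.46)) = 3.013. Power is Phi(3.013 - 1.960) = 85% unsplit, Phi(3.013 - 2.241) = 78% split over two, and Phi(3.013 - 2.394) = 73% split over three.

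**If each term is tested at .05.** The chance of at least one false positive among three independent terms is 1 - .95^3 = 14.3%. Simulation allowing for the correlation under 0/1 SNAP coding gives 10.5% to 11.9%. For the two treatment terms alone it is 1 - .95^2 = 9.75% if independent, and 7.5% to 8.9% under 0/1 coding.

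**Coding.** Let D0 and D1 be the arm differences in slope in non-SNAP and SNAP families, and p the SNAP share. With SNAP coded 0/1, the time x treatment coefficient is the effect in the reference stratum only, for instance D0. With SNAP centred at p it is (1 - p)D0 + pD1, the average over all households. If the raw 0/1 coefficient were the test, and effects were equal in both strata, power would be Phi(2.802 x sqrt(f) - 1.960), where f is the reference stratum's share: 65%, 51% and 34% for f = .7, .5 and .3. This is a worst case on assumed shares.

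**The case against.** The strongest reply is that the confirmatory term is not in real doubt. Section 5 introduces the models as a comparison of the two arms' trajectories, and sections 2 and 15 agree. That stands: a reader might infer that the trial has no primary analysis, and the documents do not support this. What remains is that the alpha rule does not follow the evident priority, and that the coefficient is undefined until the SNAP coding is given.

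A reader might also infer that alpha is to be divided by three and that power is therefore 66%. No section says so. A two-term split is at least as natural, given that time x SNAP holds no treatment effect, and a joint test is possible. The figures are also calibrated to an end-of-study difference, not to the planned model in days. They are illustrations of what each reading would cost.

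Nor do the documents show that the trial would run out of families. A three-way split multiplies the sample by ((2.394 + 0.842)/2.802)^2 = 1.33. From 120 per arm that is 160 retained, or 2 x 160/.85, about 377 recruited. At design effect 1.46, the unsplit 103.8 per arm becomes 138.4, or about 326 recruited. The pool is about 300 in section 15, called conservative there, and 350 in section 14. The lower need falls between the two. The unsplit target of about 280 would already take 93% of 300, while section 15 considers 75% and 50% enrolment. The pool does not decide the matter.

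Three smaller points are fair. A false positive on time x SNAP is not a false claim of benefit, so the two-term error rates are the more relevant ones. SNAP moderation has a rationale in section 4, so making it secondary is partly a judgement. Section 15 also sizes the as-treated analysis, on a correlation, so the argument here concerns the intention-to-treat calculation only.

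Section 4 lists "fruits and vegetable consumption, measured by SPAN, 2nd Grade" as primary, while section 5 places it among "secondary outcome measures (such as Fruits & Vegetable subscores, BMI and parent HEI". That is a separate inconsistency, and this point does not depend on it.

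**Conclusion.** The point holds, and should be fixed before the data are seen. Section 5 places an overall 0.05 on three terms, one of which carries no treatment effect, while the trial's hypothesis and intention-to-treat sample size rest on one arm difference at .05. Unless time x treatment is tested first at the full .05, either power for that difference falls below the stated 80%, to between 64% and 71% under the readings tabulated, or the overall 0.05 is not held.

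The size depends on the reading chosen, on two-sided testing, and on accepting the plan's 120 per arm as giving 80%. With the smaller design effect, the fall is from 85% to 78% or 73% for the two splits. If time x treatment is given the full .05, the planned power stands as stated. The coding figures rest on assumed SNAP shares and do not bear on the seriousness of the point. That 0/1 coding confines the coefficient to one stratum is algebra and needs no such assumption.

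**What to change.** Add to section 5, in these or similar words:

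> For child HEI the single primary intention-to-treat test is the overall time x treatment contrast across all randomised households, at two-sided alpha 0.05. It is taken from the planned mixed model with SNAP status centred at its share among randomised households (or as the equivalent stratum-weighted contrast), and is expressed as the arm difference in change from baseline at day [to be stated], the prespecified end-point day.

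Then state that time x SNAP is a covariate only, and that time x treatment x SNAP is a prespecified secondary test of effect modification, reported with the arm difference and 95% CI in each SNAP stratum. Replace the sentence that sets an overall alpha on the three terms.

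The cost is a few sentences. The planned model, the visits and the sample size do not change. The one small loss is that SNAP moderation no longer shares the primary alpha. If the investigators want it under the same error rate, it can be tested only after the primary contrast is significant, which leaves the full .05 for the arm difference.
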